### 9.2.2 Eligibility criteria

#### 9.2.2.1 Inclusion criteria

- Diagnosis of hemophilia A.
- Patients previously treated for Hemophilia A.
- Patients without previous history of inhibitors or patients with previous history of inhibitors on standard prophylaxis therapy for at least 1 year prior to study entry.
- No current evidence\* of FVIII inhibitor or clinical suspicion\*\* of FVIII inhibitor.
  - \* Evidence of FVIII inhibitor as measured by the Nijmegen-modified Bethesda assay [ $<0.6$  Bethesda units (BU/mL)] or Bethesda assay [ $<1.0$  BU/mL] in 2 on consecutive samples.
  - \*\* Documented or clinical suspicion of shortened FVIII half-life ( $<6$  hours).
- Initiation of or currently on damoctocog alfa pegol with any kind of treatment modality (on-demand, prophylaxis, or intermittent prophylaxis).
- Signed informed consent/assent.

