### 9.2.3 Rationale for specific exclusion criteria

Patients with diagnosis of any other bleeding/coagulation disorder other than hemophilia A, contra-indications according to the local marketing authorization (including patients who have history of hypersensitivity reactions to the active substance, mouse or hamster protein, or other constituents of the product and patients with active FVIII inhibitors), and patients on ITI treatment will not be included according to the labeled indication and contra-indications, as a positive benefit-risk has not been established for these patient populations.

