**Table 4: Estimated 95% confidence intervals in various scenarios**

Number of patient	95% CI	Precision based on half width of the 95% CI
36	(4.32, 8.66)	± 2.17
108	(4.92, 7.39)	± 1.23
180	(5.16, 7.07)	± 0.96

Sample size justification is further based on the need to observe a rare AE, and it is reasonable to assume that the number of patients in the safety analysis set (SAF) is close to the target enrollment (i.e., at least 200).

Table 5 presents the expected probabilities of observing a specific number of patients with events in the study under varying underlying incidence risks. The table indicates that 200 patients will provide an adequate chance of observing events with event rate larger than 2.0%, as there is a 76.5% chance of observing at least 3.

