## 9.7 Data analysis

### 9.7.1 Statistical considerations

Statistical analyses will be of an explorative and descriptive nature. The study is not aimed to confirm or reject predefined hypotheses, hence no formal hypothesis testing will be performed.

Statistical analysis of the HEM-POWR sub-study will be mostly of exploratory nature, descriptive statistics can also be applied, and will be in the statistical section of the sub-study protocol.

All variables will be analyzed descriptively with appropriate statistical methods: categorical variables by frequency tables (absolute and relative frequencies) and continuous variables by sample statistics (i.e., mean, standard deviation [SD], minimum, median, quartiles, and maximum). Continuous variables will be described by absolute value and as change from baseline per analysis time point, if applicable.

All analyses will be performed for the total study population (overall analysis). Separate analyses for individual participating countries or regions will be provided if required for local reasons when sufficient data is available.

Sample size and disposition information including reasons for discontinuation by analysis time point will be displayed in a frequency table.

All therapies documented in the following forms will be coded using the World Health Organization Drug Global.

- Prior and concomitant medication
- Prior FVII treatment

Any diagnoses/diseases/event terms documented in the following forms will be coded using the latest Medical Dictionary for Regulatory Activities (MedDRA) version:

- General medical/surgical history
- Surgeries
- Adverse events

Annual analyses are planned to provide annual safety reports and preliminary results to support publications. The final analysis will be performed after end of the study, which is the date the analytical dataset is completely available.

All statistical details including calculated variables and proposed format and content of tables will be detailed in the Statistical Analysis Plan (SAP). Bayer AG will provide oversight of data analysis activities that will be assigned to a CRO. All specific processes and technical details will be documented by the CRO statistician in the SAP and tables specification manual. The SAP will be finalized before the first database lock. The SAP is available upon request (see [Table 6](#)).

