### **9.7.3 Analysis of treatment exposure**

Analysis of treatment exposure will be performed on the SAF.

In this study, the following 4 types of exposure based on physician's prescription will be considered:

- Prophylaxis: twice weekly (including any prescription more than 7 times per month).
- Prophylaxis: every 5 days (including any prescription between >5-7 times per month).
- Other: if not listed above.
- All.

The damoctocog alfa pegol exposure will start with the first infusion in the study. The period of continuous exposure per treatment pattern (following approved local label), stops whenever prescribed damoctocog alfa pegol treatment regimen changes. Treatment patterns for non-naïve patients will also be summarized.

Exposure duration (in days) will be analyzed descriptively by summary statistics and frequency tables per treatment pattern.

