## 11.2 Collection

It should be documented in the eCRF whether the patient is participating in a registry or other program where reporting of AEs to a third party may occur in addition to the reporting requirements for this study.

Starting with the first administration of damoctocog alfa pegol after enrollment into the study, all non-serious AEs must be documented on the AE Report Form or in the eCRF/EDC system and forwarded to the Marketing Authorization Holder (MAH) within 7 calendar days (for EU countries or if required by local regulations of participating country) or 60 days (for countries outside the EU) of awareness. All SAEs must be documented and forwarded immediately (within 1 business day of awareness). For each AE, the physician must assess and document the seriousness, duration, relationship to product, action taken and outcome of the event.

If a pregnancy in the female partner of a male patient or in a female patient occurs during the study, although it is not an SAE itself, it should be documented and forwarded to the MAH within the same time limits as an SAE. The result of a pregnancy will be followed-up according to applicable Bayer standard operating procedures. Any data on abnormal findings concerning either the mother or the baby will be collected as AEs.

The documentation of any AE/SAE ends at the latest 30 days after the completion of the observation period of the patient: i.e., any AE/SAE - regardless of the relationship and the seriousness - occurring up to 30 days after the last dose of damoctocog alfa pegol within the patient's observation period has to be documented and forwarded to the MAH within the given timelines.

As long as the patient has not received any damoctocog alfa pegol within the frame of the study AEs/SAEs do not need to be documented as such in this OS. However, they are part of the patient's medical history.

For any serious product-related AE occurring after study end, the standard procedures that are in place for spontaneous reporting have to be followed.

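### For hypersensitivity, inhibitors and loss of effect, pooling current users with new starters can understate risk from initiation, and the 76.5% detection figure rests on an unstated condition

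*Protocol*

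**What the plan says.** - **Who enters.** Protocol Section 9.2.2.1 admits on the basis of "Initiation of or currently on damoctocog alfa pegol with any kind of treatment modality". It sets no limit on earlier time on the drug and no minimum number of naive patients.
- **Who does not.** Contra-indicated patients are excluded, and Section 9.2.3 spells this out as "including patients who have history of hypersensitivity reactions to the active substance"; patients with an active inhibitor are out as well.
- **When counting starts.** Section 11.2: "Starting with the first administration of damoctocog alfa pegol after enrollment into the study, all non-serious AEs must be documented". The same section treats anything before the first in-study dose as medical history. Section 9.7.3 sets the exposure clock to match: "The damoctocog alfa pegol exposure will start with the first infusion in the study".
- **What is estimated.** Section 9.7.7 reports each adverse event of special interest, on the whole safety analysis set (SAF), both as a risk and as a rate per unit of exposure. It names no split by earlier use of the drug.
- **What the study size promises.** Section 9.5, below Table 4, says that "200 patients will provide an adequate chance of observing events with event rate larger than 2.0" percent, because "there is a 76.5% chance of observing at least 3". It adds that "it is reasonable to assume that the number of patients in the safety analysis set (SAF) is close to the target enrollment".
- **Stratification.** Section 9.7.1 lists naive or non-naive status as a general stratifier. The safety tables that it specifically promises are by inhibitor history and by exposure days to FVIII product, not to this drug.

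**The concern.** A patient already on the drug at enrollment has come through some period of use without the events that would bar entry, and without stopping. Events in that earlier period are not counted. The patient then adds fully to the denominator of the pooled estimate. If the event tends to arise soon after starting, or if some patients are more susceptible than others, the pooled figure is lower than the risk faced by someone who starts the drug, and it moves with the mix of naive and non-naive patients.

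This matters because the study is a post-authorization safety study and these events are among its named safety concerns. A pooled percentage is easily read as the risk of starting the drug. The detection statement has the same weakness: it applies one risk to all 200 patients, although Section 9.7.1 itself lists time on treatment among the influencing factors.

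**Working it through.** **Inputs from the protocol.** N = 200 for safety; the 10% dropout in Section 9.5 is applied only to effectiveness. Underlying risk p = 2.0%; stated chance of at least 3 patients with the event 76.5%. The study is descriptive ("hence no formal hypothesis testing will be performed"), so there is no alpha or power to check.

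**Inputs that the protocol does not give (assumptions).** f, the share of naive patients: 75%, 50% or 25%. e, the share of the 2% risk that non-naive patients have already passed at enrollment: 0%, 50% or 100%.

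**Step 1: the plan's own figure.** P(X ≥ 3) = 1 − Σ (x = 0 to 2) C(200, x) · 0.02^x · 0.98^(200 − x) = 1 − (0.0176 + 0.0718 + 0.1458) = 0.765. This agrees with the protocol, and all 16 cells of Table 5 reproduce to three decimals.

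**Step 2: wholly early event (e = 100%).** Only the 200·f naive patients can have the event while observed.

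- 75% naive, n = 150: P(X ≥ 3) = 0.579
- 50% naive, n = 100: 1 − (0.1326 + 0.2707 + 0.2734) = 0.323, which is the protocol's own n = 100 cell
- 25% naive, n = 50: P(X ≥ 3) = 0.078

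**Step 3: partly early event.** Naive patients carry 2%, non-naive patients 2% × (1 − e). The case count is the sum of two independent binomials, and its tail was computed exactly. The pooled risk is 2% × [f + (1 − f)(1 − e)].

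| Naive share | P(≥3), e = 0% | P(≥3), e = 50% | P(≥3), e = 100% | Pooled risk, e = 50% | Pooled risk, e = 100% |
|---|---|---|---|---|---|
| 75% | 76.5% | 68.2% | 57.9% | 1.75% | 1.5% |
| 50% | 76.5% | 57.9% | 32.3% | 1.5% | 1.0% |
| 25% | 76.5% | 45.7% | 7.8% | 1.25% | 0.5% |

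**Step 4: which events the selection reaches.**

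- *Hypersensitivity to the product and an active inhibitor* are barred at entry.
- *Loss of drug effect* has no exclusion of its own, but a patient who stopped for that reason does not enter as a current user, and Section 9.2.2.1 also bars clinical suspicion of a shortened FVIII half-life.
- *Renal impairment and neurocognitive disorders* have no comparable entry filter, and nothing in the protocol places them early.

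**The case against.** The strongest reply is that the protocol gives no time to onset for any of these events. Section 7.2 calls hypersensitivity and loss of efficacy class effects and stops there. Without a falling hazard or differing susceptibility there is no understatement, and 76.5% stands. This is correct: the size of the effect is conditional and cannot be fixed from the document.

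Several stronger readings are tempting and are not supported:

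- *All five special-interest event rates are biased low.* Not shown. For renal or neurocognitive events that grow with cumulative exposure, earlier use could push the pooled figure up.
- *Nobody with an earlier reaction can enroll.* Section 9.2.2.1 admits patients with a past inhibitor after at least 1 year on standard prophylaxis. Only product hypersensitivity and active inhibitors are barred.
- *All non-naive patients are past the early period.* There is no minimum time on drug, so a recent starter may still be in it.
- *The exposure-adjusted rate is miscalculated.* Cases and person-time start together, so there is no immortal time. The rate is valid for the time observed; the error would be to read it as a rate from initiation.
- *Table 5 is wrong.* It is not. Its n = 200 cells at 1.5%, 1.0% and 0.5% (0.579, 0.323, 0.080) already lie close to the wholly early figures. What is missing is a statement of when those cells apply.

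It is also fair to say that the general stratification in Section 9.7.1 partly answers the rate problem, and that table layout belongs to the statistical analysis plan. But the detection statement is made in the protocol itself. Section 9.9 mentions selection bias only in general terms and not late entry of current users, although the checklist in Annex 2 cites that section for selection and time-related bias.

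**Conclusion.** The point holds for three events: hypersensitivity, inhibitor development and, through patients who stopped, loss of drug effect. For these, the pooled SAF incidence understates risk from initiation to the extent that risk falls with time on the drug or susceptible patients have left before enrollment. The 76.5% is correct arithmetic under a condition that the protocol does not state. Under the assumed naive shares of 75% to 25%, it becomes 57.9% to 7.8% for a wholly early 2% event and 68.2% to 45.7% for a half-early one. It is unchanged if there is no early component or if all patients are naive. A reader might infer that the safety results as a whole are biased low or that the sample size is miscalculated; the protocol supports neither conclusion. The defect is in what the pooled estimate and the detection statement can be taken to mean.

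**What to change.** - **Section 9.7.7.** Report hypersensitivity, inhibitor development and loss of drug effect by naive status. Make naive patients the main estimate of risk from initiation. Show non-naive patients separately with delayed entry at enrollment on the time-since-start scale, using the treatment start date and pre-enrollment dose dates that Section 9.3.7 already collects. Keep the pooled SAF result and label it as a description of the person-time observed.
- **Section 9.5.** Keep Table 5. Add that the 76.5% assumes that all 200 patients carry the full 2% risk while observed, and that for early-onset events the relevant number is the naive patients (for example, the n = 100 rows if half are naive).
- **Section 9.9.** Name late entry of current users as a limitation.

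**Cost.** Wording, a less favorable detection statement for early events, and wider intervals in the naive set: at a given risk, roughly √(200/100) = 1.4 times as wide if half the patients are naive. No new data and no change to eligibility are needed.

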### **9.7.4 Analysis of effectiveness variable**

Analysis of the primary outcome will be performed on the FAS, and if needed and data permits, within the subgroups defined in Section 9.7.1.

#### **ABR:**

Summary statistics of the number, type, location, and severity of reported bleeds (total, spontaneous, joint, and trauma) will be presented.

The primary analysis on ABR will be performed in patients receiving prophylactic treatment. ABRs will first be characterized using descriptive statistics by calculating mean ( $\pm$  standard deviation [SD]), median, minimum, and maximum. Further, the mean ABRs along with 95% CIs will be estimated using a negative binomial regression model corrected for over-dispersion, and with relevant treatment and disease characteristics as covariates and observed prophylactic treatment period as an offset variable.

When enough data is collected, additional analyses include: 1) comparing the ABR in patients receiving prophylactic treatment with those who are not treated with standard prophylaxis; 2) comparing the ABR in patients receiving damoctocog alfa pegol prophylactic treatment with the ABR prior to the damoctocog alfa pegol treatment.

Further details of the analysis will be described in the SAP.

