### **7.3 Background**

Prophylaxis with FVIII reduces bleeds and improves joint outcomes in patients with severe hemophilia A [11],[12],[13],[14], and it is therefore the standard of care in most developed countries [2],[15]. However, adherence to prophylaxis is poor in some patients [16]. This may be due to the high time burden and inconvenience of a typical prophylaxis regimen, which requires intravenous infusion at least 2 or 3 times per week [17],[18],[19]. Thus, prolonged-half-life FVIII products that allow for less frequent, individualized dosing may increase adherence and ultimately lead to improved clinical outcomes, including prevention of joint disease [20],[21],[22].

In a phase I study of 14 patients, damoctocog alfa pegol had a half-life of ~19 hours versus ~13 hours for sucrose-formulated rFVIII [8]. In the phase II/III PROTECT VIII study [9], median annualized bleeding rate (ABR) was 2.1 for patients using damoctocog alfa pegol twice weekly, every 5 days, and every 7 days [9], and 1.5 during the long-term extension study. Safety was comparable to that observed with other FVIII products [23],[24],[25],[26],[27]. Patients and physicians can choose from 3 effective prophylaxis regimens with damoctocog alfa pegol based on individual patient bleeding profile and lifestyle. However, there are currently no data regarding real-world use of the product outside of the clinical study.

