### **9.1.2 Secondary endpoints**

The secondary endpoints are:

- Occurrence, duration, treatment, severity, and outcome of AEs of special interest (hypersensitivity reactions, loss of drug effect, renal impairment, neurocognitive disorders, and inhibitor development), AEs, SAEs, and ARs.
- Hemostasis during surgery measured by number of infusions and consumption of FVIII product
- Change in joint scores (HJHS) from baseline to 12 months, to 24 months, to 36 months.
- Joint status evaluation by ultrasound (HEAD-US score), if available or part of standard clinical practice.
- Number of affected joints by patient, and the change from baseline to 12 months, to 24 months and to 36 months.
- Annualized number of spontaneous, joint, and trauma bleeds.
- Number of reported bleeds (total, spontaneous, joint, and trauma) during the study compared with number of reported bleeds (total, spontaneous, joint, and trauma) for previous FVIII products in the 12 months prior to enrollment into the study.
- Proportion of patients with 0 bleeds, and the difference in proportion comparing to previous prophylaxis treatment.
- Description of PK parameters for previous FVIII products versus damoctocog alfa pegol (if available in routine clinical practice).
- Efficacy of treatment of break-through bleeds.
- Change from baseline to 12 months, to 24 months and to 36 months in treatment satisfaction (Hemo-SAT A score).
- Change from baseline to 12 months, to 24 months and to 36 months in treatment satisfaction (Hemo-QoL [A and SF] score).

- Change from baseline to 12 months, to 24 months and to 36 months in work productivity and activity impairment (WPAI score).

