### 9.3.4 Hemophilia Disease history

Disease history describes any medical findings that are relevant to the underlying disease and were present before enrollment into the study. Findings and diagnoses meeting the criteria listed below have to be documented, if available:

- Date of diagnosis (at least the year).
- Type of gene mutation, if available.
- Family history of hemophilia.
- Family history of inhibitors.
- Severity of hemophilia at initial diagnosis.
- Age/age group at first treatment with factor FVIII replacement therapy.
- Age at initiation of prophylaxis therapy, if applicable.
- Duration of prophylaxis treatment lifetime.
- Patient history of inhibitors (date, high/low titer, etc.).
- ITI history.
- Most recent FVIII product (name, treatment modality [on-demand, prophylaxis, or intermittent prophylaxis], dose/regimen) up to 12 months prior to start of therapy with damoctocog alfa pegol.
- PK parameters from most recent FVIII products, if available.
- Number and location of affected joints.
- Reported previous bleeds (number, type, and location) within 12 months prior to start of therapy with damoctocog alfa pegol.
- Ultrasound scanning (Hemophilia Early Arthropathy Detection with Ultrasound [HEAD-US]) to evaluate joints of patients with hemophilic arthropathy [28].

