### **9.3.6 Prior and concomitant medication/treatments**

Medication taken /treatment received prior to study start (initiated and stopped before study start) is termed prior medication/treatment. Prior medication/treatment for hemophilia A at inclusion (on-demand, prophylaxis, or intermittent prophylaxis) received up to 12 months prior to study enrollment or initiation of damoctocog alfa pegol, whichever comes earlier are considered to be relevant to the study indication and have to be documented, if available.

All medication taken/treatment received (either initiated before study start or during the study) in addition to damoctocog alfa pegol for any indication is termed concomitant medication/treatment and has to be documented, if available.

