### **Sub-populations:**

Data will be stratified by prophylaxis dosing regimen (following approved local label, see Section 9.7.3), severity of hemophilia (mild, moderate, or severe), severity of patient bleeding profile at baseline (ABR in the last 12 months prior to enrollment), medical history (in particular joint status [affected joint: yes/no; 1 affected joint/>1 affected joint]), age groups, and time on treatment (i.e., damoctocog alfa pegol-naive or not). The prophylaxis-dosing regimen as prescribed by the physician at the beginning of the study will be used for stratification, unless otherwise stated.

Assignment of patients into treatment categories in case of changes to the regimen or switch to on-demand will be specified within SAP. Whenever reasonable, further subgroups (e.g., sex, baseline patient/disease/pre-treatment characteristics) will be specified in the SAP. Selected tables (including safety events, treatment administration and prophylaxis regimen) will be presented by history of inhibitors and exposure days (to FVIII product) at baseline.

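### The before/after ABR comparison does not separate patients by earlier treatment modality, so a move from on-demand treatment to prophylaxis can show as a reduction with no difference between products

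*Protocol*

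**What the plan says.** Section 9.7.4 (ABR) lists two additional analyses, to be done once enough data have accrued. The second is "comparing the ABR in patients receiving damoctocog alfa pegol prophylactic treatment with the ABR prior to the damoctocog alfa pegol treatment". Only the on-study side is tied to prophylaxis. The section leaves further detail to the SAP.

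Section 9.1.2 has two related secondary endpoints:

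- Bleed counts during the study are compared with counts "for previous FVIII products in the 12 months prior to enrollment into the study". Modality is restricted on neither side.
- The zero-bleed endpoint reads "Proportion of patients with 0 bleeds, and the difference in proportion comparing to previous prophylaxis treatment". Here the comparator is earlier prophylaxis only.

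Section 9.3.6 expects mixed earlier treatment: "Prior medication/treatment for hemophilia A at inclusion (on-demand, prophylaxis, or intermittent prophylaxis) received up to 12 months prior to study enrollment". Section 9.3.4 records it for each patient: "Most recent FVIII product (name, treatment modality [on-demand, prophylaxis, or intermittent prophylaxis], dose/regimen) up to 12 months prior to start of therapy". The inclusion criteria (9.2.2.1) ask for earlier prophylaxis only from patients with a history of inhibitors.

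On the effect of modality, section 7.3 says: "Prophylaxis with FVIII reduces bleeds and improves joint outcomes in patients with severe hemophilia A".

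**The concern.** A patient who moves from on-demand treatment with an older product to prophylaxis with damoctocog alfa pegol changes two things at once. By the protocol's own account, the second change lowers bleeding whatever the product. In the 9.7.4 comparison every patient is on prophylaxis afterwards, and some may not have been before, so the distortion runs one way, towards a lower ABR on the new product. In the 9.1.2 bleed-count comparison either side may contain any modality, so the same mixing occurs, but its direction depends on who changed.

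The protocol also treats its own bleed endpoints differently. The zero-bleed result and the ABR result would rest on different comparator populations and could not be read side by side.

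At stake is the meaning of a figure likely to be quoted. Section 7.2 foresees using the results to inform patients, payors and providers, and section 9.1 plans yearly interim analyses that feed publications.

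**Working it through.** **Nearest planned figure.** The protocol gives no number for the before/after comparison. The closest is the half width of ±0.96 for mean ABR at n = 180 in Table 4 (section 9.5), with mean 6 and dispersion 1. The negative binomial variance is 6 + 6²/1 = 42, and 1.96 × √(42/180) = 0.95, which agrees closely with the stated value.

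**Inputs for the illustration.**

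- Prophylaxis ABR b: 4 (the earlier trial result quoted in 9.5), with 6 (the planning value there) as an alternative. It is the same on the old and the new product, so the true product effect is 0.
- On-demand ABR A: not in the document; assumed 8, 12 or 20.
- Share p of the comparison group formerly on demand: not in the document; assumed 5%, 10% or 20%.

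**Formulas.** Earlier mean ABR = (1 − p) × b + p × A. Apparent reduction = 1 − b / earlier mean.

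Results (earlier mean, then apparent reduction):

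| b | p | A = 8 | A = 12 | A = 20 |
|---|---|---|---|---|
| 4 | 5% | 4.2, 5% | 4.4, 9% | 4.8, 17% |
| 4 | 10% | 4.4, 9% | 4.8, 17% | 5.6, 29% |
| 4 | 20% | 4.8, 17% | 5.6, 29% | 7.2, 44% |
| 6 | 10% | 6.2, 3% | 6.6, 9% | 7.4, 19% |

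Worked example: b = 4, A = 20, p = 20% gives 0.8 × 4 + 0.2 × 20 = 7.2, and 1 − 4/7.2 = 44%.

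**Against the plan's precision.** The earlier mean shifts by p × (A − b). With b = 4 it shifts by 0.96 when p = 0.96/(A − 4), which is 24%, 12% or 6% for A = 8, 12 or 20. This is only a yardstick: 0.96 is the half width for a single mean at mean 6, not for a within-patient difference.

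**After the change.** With the comparator limited to earlier prophylaxis, p = 0, the earlier mean equals b, and the apparent reduction is 0.

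**Do other provisions already separate modality?**

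- The named strata in section 9.7.1 include "severity of patient bleeding profile at baseline (ABR in the last 12 months prior to enrollment" but not prior modality. Prior ABR is no substitute: a high value may come from on-demand treatment or from poorly controlled prophylaxis.
- The same section lets the SAP add subgroups on pre-treatment characteristics where reasonable. That permits the split but does not commit to it.
- The confounding text in 9.7.1 names pre-treatment history as an example covariate, to control differences between groups. Adding a baseline covariate does not by itself remove a modality change from a within-patient contrast; restriction or stratification does.
- The limitations in section 9.9 cover confounding and channelling bias in general, but not a change of modality in the before/after comparison.

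**The case against.** The strongest reply is that this is one conditional, descriptive analysis whose detail is expressly left to the SAP. Section 9.7.1 allows subgroups on pre-treatment characteristics, and prior modality is on file, so the SAP may well split by it. The protocol nowhere says that modalities will be pooled. Change in ABR from whatever went before is also a legitimate descriptive quantity if labelled as such.

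Most of that is fair, and it limits the weight of the point. It does not dispose of it. The protocol set the comparator for the zero-bleed endpoint itself and set a looser one for ABR. Calling the analysis descriptive does not remove the mixing from the figure.

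On size, the reply also has force. Sections 7.3 and 9.2.6 describe prophylaxis as standard care in most developed countries and in severe disease, so the on-demand share may be small. Medians, which 9.7.4 also reports, would move much less than means. The low end of the range is therefore as relevant as the high end.

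Three stronger readings are tempting, and the document does not support them:

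- A reader might infer that the protocol will present the difference as a product benefit. It does not say so. The primary objective concerns the effectiveness of prophylaxis, and section 9.7.1 rules out formal testing.
- A reader might take this as the only comparison with earlier products. Section 9.1.2 also has the bleed-count, zero-bleed and PK comparisons.
- A reader might take the modality list in the eligibility criteria as describing earlier treatment. It describes treatment with damoctocog alfa pegol; earlier modality appears in sections 9.3.4 and 9.3.6.

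**Conclusion.** The point holds as a weakness in the choice of comparator. As written, the 9.7.4 ABR comparison restricts modality on one side only, and the 9.1.2 bleed-count endpoint restricts it on neither. A pooled 9.7.4 result can show a fall in mean ABR with no product difference.

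Across the scenarios shown, the spurious fall runs from 3% to 44%. The range rests on an assumed on-demand share, an assumed on-demand ABR, and equal prophylaxis ABR on both products. It covers mean ABR only, and leaves out patients formerly on intermittent prophylaxis, for whom the document gives no rate. Nothing here shows how large the effect will be in this cohort.

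The primary endpoint is untouched. This is a cheap improvement to a secondary endpoint and an additional analysis, not a fault that undermines the study.

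**What to change.** In sections 9.1.2 and 9.7.4, state that the main before/after comparison of bleeds and ABR is made in patients on damoctocog alfa pegol prophylaxis whose most recent FVIII treatment was also prophylaxis, in line with the comparator of the zero-bleed endpoint. Report patients who came from on-demand treatment or intermittent prophylaxis separately, labelled as a change of modality, and do not pool them with the main group.

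This takes about two sentences and no new data, because section 9.3.4 already collects "Most recent FVIII product (name, treatment modality [on-demand, prophylaxis, or intermittent prophylaxis], dose/regimen) up to 12 months" before the start of damoctocog alfa pegol. The cost is fewer patients, and so wider intervals, in the main before/after comparison. The number in each group should be shown.
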